1.7 Justification for the study

This research is needed now because the uncertainties have led to current practice that is highly variable, and a proliferation of non-evidenced based guidelines. Parents, patients (those living with the long-term consequences of neonatal conditions), clinicians, and the James Lind Priority Setting Partnership have repeatedly ranked identification of enteral feeding strategies that reduce NEC a priority for well over a decade (17-19).

The NICE guidance “*Donor milk banks: service operation*” acknowledges the limited high-quality evidence for use of pHDM and includes the recommendation for research to evaluate efficacy in improving outcomes and identify babies who would benefit most (20). The 2023 British Association of Perinatal Medicine “*Framework for use of Donor Milk*” also highlights the urgent need for this research (21). The American Academy of Pediatrics and European Society for Paediatric Gastroenterology, Hepatology and Nutrition only conditionally support use of pHDM as the supplementary feed of choice, acknowledging the benefits of Own Mother’s milk over pHDM, the variable nutrient content and uncertain non-nutrient benefits of pHDM, and the limited evidence-base for practice.

2 OBJECTIVES AND ENDPOINTS

2.1 Primary objectives

- To assess, in babies born <29 weeks gestation, the efficacy of pHDM compared with Preterm Formula when used as a supplement should there be insufficient milk from their own mother (Own Mother’s Milk) on “survival to 34 weeks postmenstrual age without surgical NEC”
- To assess, in babies born <29 weeks gestation, if routine cow-milk based protein-carbohydrate fortification of human milk feeds (Own Mother’s Milk and pHDM) compared with no routine fortification, affects “survival to 34 weeks postmenstrual age without surgical NEC”

Title: COLLABORATE	EDGE No: 181495	Sponsor: Imperial College London	Version: 3.0; 09/01/2026
---------------------------	---------------------------	--	---------------------------------

2.2 Secondary objectives

- To assess the efficacy of pHDM compared with Preterm Formula on language and cognitive development at age 2-years, and other outcomes in babies born <29 weeks gestation, when used as a supplement should there be insufficient milk from their own mother (Own Mother's Milk)
- To assess if routine cow-milk based protein-carbohydrate fortification of human milk feeds (Own Mother's Milk and pHDM) in babies born <29 weeks gestation affects language and cognitive development at age 2-years, and other outcomes

2.3 Tertiary objectives

- To determine if pHDM and Preterm Formula exert different effects on neurodevelopment through the mechanism of altered cerebral white matter microstructure.
- To establish if the additional cost of pHDM to the NHS is justified through a reduction in NEC
- To establish if the additional cost of fortifier, generates savings through improved survival to age two-years corrected for prematurity without moderate-severe cognitive-language impairment
- To collect and store faecal samples from participants recruited in Edinburgh who are enrolled in randomisation 1, for future mechanistic studies subject to funding

2.4 Endpoints

2.4.1 Primary

Assessed at 34 weeks postmenstrual age

- Survival without surgical NEC

2.4.2 Secondary

Assessed at 34 weeks postmenstrual age

- Survival
- Surgical NEC
- Spontaneous Intestinal Perforation

Assessed at 36 weeks postmenstrual age

- Bronchopulmonary dysplasia

Assessed at postnatal age 28 days

- Survival

Assessed at neonatal unit discharge (or death)

- Survival
- Surgery for NEC or NEC related condition after 34 weeks postmenstrual age
- Medical NEC
- Age in days to achieve an enteral intake of 150 ml/kg/day
- Treated retinopathy of prematurity

Title: COLLABORATE	EDGE No: 181495	Sponsor: Imperial College London	Version: 3.0; 09/01/2026
---------------------------	---------------------------	--	---------------------------------

- Severe brain injury
- Any diagnosis of milk-curd obstruction
- Length of neonatal unit stay
- Number of episodes of bacterial or fungal bloodstream infection
- Number of episodes of bacterial or fungal cerebrospinal fluid infection
- Number of episodes of bacterial or fungal urinary tract infection
- Number of days of antibiotic treatment
- Number of days on parenteral nutrition
- Number of days nil by mouth
- Weight, length, and head circumference Z-scores
- Change from birth in Z-scores for weight, length, and head circumference
- Any breast feeding (suckling at breast)
- Exclusive breast feeding (suckling at breast)
- Receiving any expressed Own Mother's Milk
- Receiving exclusive expressed Own Mother's Milk
- Maximum serum urea, creatine, and alkaline phosphatase
- Health resource use

Assessed at neonatal unit discharge (or death) in babies with NEC surgery

- Drain insertion prior to surgery (yes/no)
- Diagnosis of short bowel syndrome (yes/no)
- Diagnosis of intestinal failure-associated liver disease (yes/no)
- Length of bowel resected (cm)
- Primary surgical procedure (ileostomy; colostomy; end-to-end anastomosis)
- Number of re-operations (excluding primary operation)

Assessed at age 2-years corrected for prematurity

- Survival without moderate-severe cognitive-language impairment
- Survival
- Moderate-severe cognitive-language impairment
- Cognitive sub-score
- Language sub-score
- Gross motor function
- Hearing impairment
- Vision impairment

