1.3.1 Randomised trial hypotheses

- In babies born <29 weeks gestation for whom there is need to supplement Own Mother's Milk because the volume available is insufficient (P), pHDM (I), when compared with Preterm Formula (C), improves survival rate to 34 weeks postmenstrual age without surgical NEC (PO).
- In babies born <29 weeks gestation (P), routine macronutrient fortification of human milk (Own Mother's Milk and pHDM) with cow milk fortifier (I), when compared with no routine fortification (C), improves survival rate to 34 weeks postmenstrual age without surgical NEC (PO).

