	
 Survival Surgery for NEC or NEC related condition after 34 weeks postmenstrual age Medical NEC Age in days to achieve an enteral intake of 150 ml/kg/day Treated retinopathy of prematurity Severe brain injury Any diagnosis of milk-curd obstruction Length of neonatal unit stay Number of episodes of bacterial or fungal bloodstream infection Number of episodes of bacterial or fungal cerebrospinal fluid infection Number of episodes of bacterial or fungal urinary tract infection Number of days of antibiotic treatment Number of days on parenteral nutrition Number of days nil by mouth Weight, length, and head circumference Z-scores Change from birth in Z-scores for weight, length, and head circumference Any breast feeding (suckling at breast) Exclusive breast feeding (suckling at breast) Receiving any expressed Own Mother's Milk Receiving exclusive expressed Own Mother's Milk Maximum serum urea, creatine, and alkaline phosphatase Health resource use 	Neonatal unit discharge (or death)

Title: COLLABORATE	EDGE No: 181495	Sponsor: Imperial College London	Version: 3.0; 09/01/2026
---------------------------	---------------------------	--	---------------------------------

	
 • Survival without moderate-severe cognitive-language impairment • Survival • Moderate-severe cognitive-language impairment • Cognitive sub-score • Language sub-score • Gross motor function • Hearing impairment • Vision impairment 	Age 2-years corrected for preterm birth
In babies with NEC surgery	
 • Drain insertion prior to surgery • Diagnosis of short bowel syndrome • Diagnosis of intestinal failure-associated liver disease • Length of bowel resected (cm) • Primary surgical procedure (ileostomy; colostomy; end-to-end anastomosis) 	Neonatal unit discharge (or death)
In babies with NEC surgery	
 • Number of re-operations (excluding primary operation) 	Age 2-years corrected for preterm birth
Tertiary		

 • To determine if pHDM and Preterm Formula exert different effects on neurodevelopment through the mechanism of altered cerebral white matter microstructure 	
 • Cerebral white matter microstructure 	Term equivalent age (37-44 weeks postmenstrual age)

Title: COLLABORATE	EDGE No: 181495	Sponsor: Imperial College London	Version: 3.0; 09/01/2026

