7 STATISTICAL ANALYSES

7.1 Statistical Analysis Plan

We will construct a detailed Statistical Analysis Plan, signed off by the Chief Investigators and Trial Steering Committee prior to the first interim analysis. We will summarise baseline characteristics by randomisation arm within each comparison using appropriate statistical measures (mean, standard deviation; median, interquartile range; frequencies; percentages). The flow of participants through both comparisons will be reported according to the CONSORT Extension for Adaptive Designs (32). We will target a treatment policy estimand to estimate the effect of each intervention as delivered in practice regardless of any events that occur post-randomisation. The efficacy and safety analyses for both randomisations will be based on the intention-to-treat population. Missing data is expected to be very low as this is retrieved from NNRD. It is specified in the Parent Information Leaflet that should they withdraw consent for their baby's participation, data already available in the NNRD will be utilised.

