7.2 Sample size and power

7.2.1 Main study

This is a group-sequential trial with 2 interim and 1 final analysis (i.e., an adaptive trial), hence the sample size is not fixed. The maximum sample size is 3252, (n=2168 in each randomisation; n=1084 per arm) assuming no early stopping, estimated on the composite primary efficacy outcome (survival to 34 weeks gestational age without surgical NEC (Y/N)).

Title: COLLABORATE	EDGE No: 181495	Sponsor: Imperial College London	Version: 3.0; 09/01/2026
---------------------------	---------------------------	--	---------------------------------

For the randomisation 1 (pHDM vs Formula supplement) an observational analysis of NNRD data estimated the difference in the proportion surviving to 34w PMA for babies born <29 weeks' gestation to vary between 0.18 and 0.52 depending on week of gestational age (favouring supplementation with preterm formula) (6) For the sample size calculation we targeted a highly conservative MCID in this proportion of 0.05 based on a baseline of 0.82 which we accurately estimated from the NNRD for this population of babies in the UK (i.e. from 0.82 to 0.87).

For randomisation, 2 (fortifier vs no routine fortifier) an unpublished observational analysis from NNRD data estimated the difference in proportion data surviving to 34w PMA for babies born <29 weeks gestation to vary between 0.06 and 0.75 depending on week of gestational age (favouring fortifier). Taking a conservative approach and in line with the first comparison, we have chosen to target the same MCID of 0.05.

We have calculated power based on a fixed sample size of 3252 unique babies using rpact (33) where interim timings were chosen to minimise the expected sample size. We anticipate at least 50% of babies will be co-enrolled into both randomisations. If co-enrolment is higher, power will increase. We have used an O'Brien & Fleming design with two-sided overall significance level of 5% to account for two interims at 50% and 75% and a normal approximation assumption for rates. For both randomisations we have factored in 2% missing outcome data due to carers withdrawing consent from routine data collection in NNRD.

Based on all the above assumptions, n=3252 (n=2168 in each randomisation and n= 1084 per arm) will achieve a minimum of 87% power for each randomisation. The expected sample size across for each randomisation is n=2439.

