7.3 Primary endpoint analysis

We will model the main intervention effect for each randomisation separately. For both, we will use a binomial Generalized Estimating Equation (GEE) model with identity link and a log link function to estimate adjusted risk difference and adjusted risk ratio (in line with CONSORT reporting recommendations) with robust variance. This will enable us to account for within network correlations. Intervention effect for the first and second randomisation will be modelled separately. Both models will be adjusted for minimisation variables.

The analysis model for randomisation 1 will include whether or not an infant received fortification (Y/N) and whether or not they were randomised to this (randomisation 2; Y/N)). Though randomisation 2 will occur after randomisation 1, they are close in time and receiving fortification may be more likely to be a predictor of the primary outcome than a result of taking part in randomisation 1. Therefore, randomisation 2 and receipt of fortification will be treated as baseline covariates.

The analysis model for randomisation 2 will include adjustment for taking part in randomisation 1 (Y/N) and type of supplementary feed received (pHDM or formula). A supplementary analysis for randomisation 2 will be performed to determine the effect of rescue fortification in the standard of care arm (no routine fortification) will be undertake using principal stratum and complier average causal effect approaches (no rescue fortification is defined as a complier in the standard of care arm). In the unlikely case that missing data are greater than 2%, a sensitivity analysis will be performed using multiple imputation.

Title: COLLABORATE	EDGE No: 181495	Sponsor: Imperial College London	Version: 3.0; 09/01/2026
---------------------------	---------------------------	--	---------------------------------

Binary secondary and key safety outcomes (death, surgical NEC, medical NEC, infection) will be analysed using the same principled approach as the primary outcome. The age 2-year PARCA-R will also be evaluated as a continuous outcome and the between arm mean difference estimated using the GEE model with normal distribution and identity link function adjusting for minimisation variables.

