7.7 Safety analyses

We will tabulate adverse events by intervention arms for each randomisation. For safety events of special interest (death, surgical NEC, medical NEC, infection) we will follow the principle of the primary analysis. For all other events we will calculate the incidence rate ratio and present these graphically using dot plots.

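### Short bowel syndrome and intestinal failure-associated liver disease are defined only in babies who had NEC surgery, so a between-arm contrast is not protected by randomisation

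*Protocol*

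**What the plan says.** Section 2.4.2 heads one block of secondary endpoints "Assessed at neonatal unit discharge (or death) in babies with NEC surgery". The block has six items: drain insertion, short bowel syndrome, intestinal failure-associated liver disease, length of bowel resected, primary procedure and number of re-operations. The first three are yes/no. The table in 2.5 repeats the restriction ("In babies with NEC surgery"). Neither place calls the block descriptive.

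On analysis, 7.3 states: "Binary secondary and key safety outcomes (death, surgical NEC, medical NEC, infection) will be analysed using the same principled approach as the primary outcome". Section 7.7 uses the same four events again: "For safety events of special interest (death, surgical NEC, medical NEC, infection) we will follow the principle of the primary analysis".

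Section 7.1 targets a treatment policy estimand, "regardless of any events that occur post-randomisation", and adds: "The efficacy and safety analyses for both randomisations will be based on the intention-to-treat population". The hypotheses in 1.3.1 are that each intervention improves survival to 34 weeks without surgical NEC. Principal stratum methods appear in 7.3 only for rescue fortification in randomisation 2.

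**The concern.** Randomisation makes the arms comparable at entry. It does not make the operated babies in one arm comparable with those in the other if the feed affects who needs surgery, and an effect on surgery is part of what the trial is looking for.

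Three misreadings become possible for short bowel syndrome and intestinal failure-associated liver disease:

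- A feed that prevents mild and severe surgical disease equally shows no effect on the sequela, although fewer babies have it.
- A feed that prevents mainly mild surgical disease leaves a sicker operated group and looks harmful.
- A feed that adds surgical cases of average severity looks neutral, although more babies have the sequela.

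Drain insertion is also binary and sits in the same block, so the same reading of 7.3 would give it the same between-arm model.

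**Working it through.** **Plan's own figures.** The protocol gives no rate, effect or power for these endpoints, so there is no figure to reproduce. The nearest one, 87% power for the primary outcome, is not affected: a group-sequential simulation with the 7.4 boundaries and 1084 × 0.98 = 1062 babies per arm gives 88.3% to 88.4%.

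**Inputs from the protocol**

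- 7.2.1: "we targeted a highly conservative MCID in this proportion of 0.05 based on a baseline of 0.82", rising to 0.87.
- 1.5.3 (observational, fortifier): the composite differs by 15.1 points and surgical NEC by 1.4 points.
- 1.5.2 (observational, donor milk v formula): surgical NEC twice as high with donor milk.
- 1.4: about 260 NEC deaths and/or surgeries per roughly 3000 births, 260/3000 = 8.7%. This counts deaths as well, so it serves only as a rough upper value for surgery.

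**Assumed.** The comparator NEC surgery rate is taken as 4% to 8.7%. All sequela counts below are assumed. Ratios observed or targeted for surgery by 34 weeks are carried to surgery by discharge.

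**Step 1: which analysis applies.** The four events bracketed in 7.3 are the same four that 7.7 calls safety events of special interest. The bracket therefore most naturally qualifies the key safety outcomes, and binary secondary outcomes as a class go to the primary model. If the bracket instead lists every outcome meant, the two sequelae have a restricted population and no stated model.

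**Step 2: the identity.** If a sequela is counted only after NEC surgery, then in each arm

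P(surgery and sequela) = P(surgery) × P(sequela given surgery).

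Dividing one arm by the other gives

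RR within surgery = RR in all randomised ÷ RR of surgery.

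For crude risk ratios this holds whatever the sequela rate. The distortion factor is 1 ÷ RR of surgery.

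**Step 3: the factor under different inputs**

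| Input | RR of surgery | Factor |
|---|---|---|
| Feeds do not change surgery | 1 | 1 |
| Fortifier share applied to the 5-point difference: 1.4/15.1 = 0.093; 0.093 × 5 = 0.46 points; comparator 8.7% | (8.7 − 0.46)/8.7 = 0.947 | 1.06 |
| Same, comparator 4% | (4 − 0.46)/4 = 0.885 | 1.13 |
| Full 1.4-point fortifier difference, comparator 8.7% | (8.7 − 1.4)/8.7 = 0.84 | 1.19 |
| Same, comparator 4% | (4 − 1.4)/4 = 0.65 | 1.54 |
| Surgery falls in proportion to the composite, failure 18% to 13% | 0.13/0.18 = 0.722 | 1.38 |
| Twofold donor-milk ratio, formula relative to donor milk | 0.5 | 2 |

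**Step 4: what this looks like in counts.** Take 1062 per arm and the proportional case, with 72 v 52 babies operated (6.8% v 4.9%).

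- Equal prevention, short bowel 18 v 13: within surgery 25.0% v 25.0%, RR 1.00 (95% CI 0.54 to 1.86). In all randomised, 1.69% v 1.22%, RR 0.72 (0.36 to 1.47).
- Only mild cases prevented, short bowel 18 v 18: within surgery 25.0% v 34.6%, RR 1.38 (0.80 to 2.39). In all randomised, RR 1.00 (0.52 to 1.91).

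Every interval includes 1. The point estimate is displaced, but with so few events a significant false result is unlikely.

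**The case against.** **No between-arm comparison is fixed.** Section 2.4.2 says when and in whom items are assessed. It names no effect measure, the sentence in 7.3 is ambiguous, and the block may be meant only to describe surgical cases. The ambiguity stands, and a reader should not infer that the protocol unequivocally commits to a within-surgery model. But nothing labels the block descriptive, and the comparison with 7.7 favours the wider reading.

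**Section 7.1 already supplies the right denominator.** Under intention-to-treat one could count the sequelae over all randomised babies. That requires setting aside a population stated in both 2.4.2 and 2.5, so the protocol conflicts with itself here and is not merely leaving detail to the SAP.

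**The distortion may be small.** This stands. A reader might infer a 38% or twofold distortion. The first assumes that surgery falls in proportion to a composite that also contains death, whereas in the protocol's own fortifier data surgical NEC made up only 1.4 of 15.1 points. The second rests on data that the protocol itself says may be confounded. Both observational analyses covered very preterm infants, not only births before 29 weeks.

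**The consequence is limited.** This also stands. Surgical NEC, surgery after 34 weeks and survival are secondary endpoints without the restriction, and a reader given counts by arm could recover the crude all-randomised rates. No stopping rule, power figure or primary conclusion is touched. This limits misreading but does not correct a published within-surgery estimate.

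**Conclusion.** The point holds as a should-fix matter on secondary endpoints. As written, the protocol defines short bowel syndrome and intestinal failure-associated liver disease in a subset formed after randomisation, and most naturally sends them to the between-arm model, at odds with 7.1. The direction and form of the bias follow from an identity. Its size cannot be fixed from the document. There is none if feeds do not change surgery; the factor is about 1.06 to 1.13 if the fortifier data's share of surgical NEC carries over to the minimum important difference, 1.38 if surgery falls in proportion to the composite, and up to 2 on the donor-milk data. These values rest on assumed surgery rates of 4% to 8.7% where a rate is needed.

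The material does not support a claim that the trial is likely to report significant false harm or false benefit. Nor does it show that drain insertion, length resected, procedure type or re-operations are wrong endpoints. They describe operated babies and need only be marked as descriptive.

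**What to change.** In 2.4.2, 2.5 and 7.3:

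1. Define the two sequelae as *NEC surgery followed by short bowel syndrome* and *NEC surgery followed by intestinal failure-associated liver disease*. Estimate their between-arm effects in all randomised babies, with no NEC surgery coded as no.
2. Show death to discharge by arm beside each estimate, because a baby who dies unoperated is otherwise counted as free of the sequela.
3. State that all within-surgery items, including the binary drain insertion item and any within-surgery sequela percentages, are summarised by arm with no treatment-effect estimate.
4. Reword the 7.3 sentence so that it is clear which binary secondary outcomes receive the primary model.

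A sensitivity analysis of death or the sequela is optional. With mortality to discharge around 10% (6.8), death would dominate it. At an assumed 106 deaths per arm, none among the short bowel cases, the equal-prevention example becomes 124 v 119, RR 0.96 (0.76 to 1.22).

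The cost is wording only. Surgery status, the diagnoses and survival are already planned data, and the change can be made before the SAP is signed off ahead of the first interim analysis. The absolute rates reported will be lower, which needs a line of explanation.

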2.4.3 Tertiary

Assessed at term-equivalent age (37-44 weeks postmenstrual age)

- Cerebral white matter microstructure indexed by fractional anisotropy values using tract-based spatial statistics

Assessed at neonatal unit discharge (or death)

- In-hospital healthcare costs

Assessed at age two-years (corrected for prematurity)

- Healthcare costs (subject to additional funding)

Title: COLLABORATE	EDGE No: 181495	Sponsor: Imperial College London	Version: 3.0; 09/01/2026
---------------------------	---------------------------	--	---------------------------------

